Treatment plan: Pinometostat will be given IV starting on day 1 at one of two doses in the phase 1b portion, and at a single defined dose (RP2D) in the phase 2 portion. Pinometostat will continue as a continuous IV infusion through day 35. A bone marrow biopsy will be performed on day 8 to assess the single agent activity. On day 8, standard of care 7+3 with cytarabine and daunorubicin will be initiated. One re-induction attempt is permitted if no CR or CRi is achieved by day 21 (day 14 of 7+3). No further study treatments (e.g. consolidation or maintenance) are planned, and patients should be consolidated as per standard of care.

Phase: 1b, 2

SCHEMA

This study is a multi-site phase 1b/2 study designed to confirm a safe and tolerable dose of pinometostat and to gauge preliminary evidence of efficacy when given as lead-in prior to and contemporaneous with standard intensive induction therapy for newly diagnosed AML with MLL rearrangement. There will be a brief safety run-in phase exploring two dosing schemes, followed by a phase 2 efficacy expansion. The phase 2 expansion will use the higher dose-level of the two schedules if tolerated (see definitions below), otherwise, the lower dose-level if tolerated. The phase 1b/safety run-in portion will have a primary endpoint of Dose-limiting Toxicity (DLT; defined below), while the phase 2 portion will have a primary endpoint of complete remission attainment, and will gather additional laboratory correlative data.

[figure not shown]

Figure 1: Abbreviated Trial Schema (Depicting Initial Induction. Re-induction resets calendar; see details)

Phase 1b/safety run-in phase

The phase 1b portion will operate according to Figure 1. Up to two cohorts will be accrued in order to identify a maximum tolerated dose for expansion. Dose escalation will occur in the standard cohorts-of-3/3+3 design. With only two cohorts (dose levels), escalation stops after cohort 2; if 2-3/3 DLT are observed at dose level 1 (cohort 1), a safety review will be initiated to decide whether dose level reductions below the starting dose should be considered.

Phase 2/expansion phase

The phase 2 portion will use the maximum tolerated dose/schedule and accrue additional patients to gather preliminary evidence of efficacy. Patients will be treated in the same manner as in the phase 1b portion above, with the exception that only a single dose level/cohort will be expanded.

Re-induction

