1. OBJECTIVES

1.1 Primary Objectives

- 1.1.1 Determine a safe and tolerable schedule of pinometostat continuous intravenous infusion in combination with daunorubicin and cytarabine in patients with untreated, newly diagnosed acute myeloid leukemia harboring MLL rearrangement
- 1.1.2 Determine the rate of complete remission (CR, CRi) in patients with newly diagnosed acute myeloid leukemia harboring MLL rearrangement after treatment with pinometostat in combination with daunorubicin and cytarabine

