2.4 Rationale

MLL-r AML occurs more commonly in younger AML patients (15% among patients less than age 60) compared to older patients (only about 2% among patients aged greater than 60 years) and as a high-risk disease subset is typically treated with 7 + 3 induction, 0-1 cycles of consolidation (depending on donor status), and then allogeneic stem cell transplant. Patients who relapse, or patients who were primary refractory, have leukemias enriched for mutations in pathways (e.g. RAS/ERK, or PTPN11/STAT) that render the cells insensitive to inhibition of Syk signaling or epigenetic silencing by DOT1L inhibition. Accordingly, we have observed a higher response rate among front line patients compared to relapsed or refractory patients in response to SYK inhibition (unpublished observation), and would anticipate a similar scenario with DOT1L inhibition. Overall, relapsed and refractory patients represent a small heterogeneous population with induction failure or relapse after transplant, in both cases likely enriched for mutations conferring resistance to targeted therapies, and do not represent an ideal population in which to administer a targeted therapy due to the risk of missing an agent with up-front activity. For any agent, the heterogeneous and poorly understood relapsed/relapsed population represents a very challenging drug development and registration strategy, whereas development could potentially be pursued more systematically and rationally in newly diagnosed patients.

To further understand newly diagnosed MLL-r patients, we examined records from 118 historical cases of MLL-r AML treated on CALGB/Alliance cooperative group clinical trials. Patients less than age 60 have only a 64% CR rate with 7+3 induction/5+2 re-induction (if necessary; *Mims et al: publication in preparation*). This CR rate is significantly below what can be achieved by other subgroups, and patients who fail to achieve CR are less likely to move to transplant and overall are more likely to die sooner of their disease. Therefore, there is a significant opportunity to show clinical benefit in this previously untreated patient population by adding another agent to 7+3 chemotherapy.

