9. STATISTICAL CONSIDERATIONS

9.1 Study Design/Endpoints

This study is a multi-site phase 1b/2 study designed to confirm a safe and tolerable dose of pinometostat and to gauge preliminary evidence of efficacy when given as lead-in prior to and contemporaneous with standard intensive induction therapy for newly diagnosed AML with MLL rearrangement. The study design involves a brief safety run-in phase exploring two dosing

schemes, followed by a phase II efficacy expansion. The phase II expansion will use the higher dose-level of the two schedules if tolerated (see definitions below), otherwise, the lower dose-level if tolerated. The phase 1b/safety run-in portion will have a primary endpoint of dose limiting toxicity, while the phase 2 portion will have a primary endpoint of complete remission / complete remission with incomplete count recovery attainment, and will gather additional laboratory correlative data.

The phase 1b safety run-in phase involves dividing patients into two cohorts (cohort 1 and cohort 2) after appropriate screening. The goal will be to identify a maximum tolerated dose for expansion. Dose escalation will occur in the standard cohorts-of-3/3+3 design, which is described below. Cohort 1 will comprise of 3-6 patients and will be treated with pinometostat 90 mg/m² continuous IV infusion (CIVI) on days 1-7, then decrease dose to 60 mg/m² CIVI for days 8-35, along with daunorubicin 60 mg/m² daily on days 8-10 and cytarabine 100 mg/m² CIVI on days 8-14. Cohort 2 will comprise of 3-6 patients and will be treated with pinometostat 90 mg/m² CIVI on days 1-35, along with daunorubicin 60 mg/m² daily on days 8-10 and cytarabine 100 mg/m² CIVI on days 8-14.

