The primary efficacy objective is to calculate the rate of complete response (CR) or complete response with incomplete count recovery (CRi) after combination treatment and the primary efficacy hypothesis is that the rate of CR will be higher than among historical controls.

H0: The CR rate is $\leq 65\%$

Ha: The CR rate is $\geq 85\%$

We will use a Simon two-stage design (minimax) to test the hypothesis that the CR rate is greater than 65%. Assuming that the true CR rate among those treated is at least 85%, and setting type I and type II error rates to 10% (yielding $\alpha=\beta=0.1$), we will enroll 13 patients in the first stage. If 8 or fewer responses are observed during stage 1, the study will be stopped early. If there are 9 or more responses, an additional 18 patients will be enrolled in stage 2 for a total of 31 patients. At the completion of the second stage, the drug will be declared efficacious and the probability of an unacceptable CR rate $\leq 64\%$ ruled out if at least 24 CRs are observed out of all 31 patients. This design has a 90% power to correctly rule out a CR rate $\leq 65\%$ if the true rate is 85%, with a type 1 error rate of 0.0951.

| | |
|-----------|----|
| N | 31 |
| n1 | 13 |
| r1 | 8 |
| n2 | 18 |
| r2 | 23 |

NOTE: Patients treated at the maximum tolerated dose in the phase 1b portion (3, or 6) will be counted toward the total needed to satisfy the statistical design. This means that possible total accrual ranges for the whole trial are not $[6, 12+31] = [6, 43]$ but $[6, 12 + 31 - 6] = [6, 37]$

For both phases, early response evaluation will occur at day 21 (day 14 of 7+3) with a bone marrow examination, and if $> 5\%$ myeloid blasts are seen, or $\leq 5\%$ myeloid blasts but with an

aberrant immunophenotype matching the pretreatment immunophenotype, a re-induction attempt may be made with 5 and 2 days of cytarabine and daunorubicin, respectively, both medications at the same doses as initial induction. Pinometostat will be given at 90 mg/m², unless 60 mg/m² was previously established as the RP2D, in which case it shall be given at 60 mg/m². The clock will be reset, and pinometostat will be administered for an additional 28 days (unless stopped early for reasons of toxicity, withdrawal from study, or death).

Exploratory pharmacodynamics biomarkers will be collected at screening, at day 8, and at relapse if applicable for both phases (these are described above).

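### The primary endpoint is CR or CRi, but the null and final success rule are written for CR and the 64% benchmark is not said to include CRi, so the 0.0951 type I error is not tied to the declared endpoint

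*Combined protocol and SAP*

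**What the plan says.** **Endpoint and objective: CR or CRi.**
- Section 1.1.2: "Determine the rate of complete remission (CR, CRi) in patients with newly diagnosed acute myeloid leukemia harboring MLL rearrangement".
- Section 9.1, opening: "the phase 2 portion will have a primary endpoint of complete remission / complete remission with incomplete count recovery attainment".
- Section 9.1, design paragraph: "The primary efficacy objective is to calculate the rate of complete response (CR) or complete response with incomplete count recovery (CRi) after combination treatment".

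**Hypothesis and decision rule: CR.** The sentence in 9.1 that gives the objective as CR or CRi goes on to say that "the primary efficacy hypothesis is that the rate of CR will be higher than among historical controls". H0 (65% or lower) and Ha (85% or higher) are both stated for the CR rate. The final rule asks for 24 or more CRs among 31 patients. The stage 1 rule (stop at 8 or fewer of 13) counts responses, a term that 9.1 does not define. The Schema also names only CR: "the phase 2 portion will have a primary endpoint of complete remission attainment".

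**Benchmark.** The one historical figure is in 2.4: "Patients less than age 60 have only a 64% CR rate with 7+3 induction/5+2 re-induction". It comes from a review of 118 cooperative-group cases. The protocol does not say whether CRi was counted, and gives no CRi rate for standard induction. Section 9.1 uses both 65% and 64% as the rate to be ruled out.

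**Definitions.** Section 12.1 lists CR and CRi as separate categories. The response categories in 9.4.2 include complete and partial response but have no place for CRi.

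**The concern.** In the same patients, the CR/CRi rate cannot be lower than the CR rate. If the 64% is CR alone, the no-effect rate for the declared endpoint is 64% plus whatever share of patients reach CRi on standard induction. The 65% null leaves one point of room for that share.

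Two things are at stake. The first is the error rate of the go/no-go conclusion, which holds at 0.0951 only if 65% is the right null for the responses being counted. The second is pre-specification. While the text supports both counts, one or two CRi patients could turn 23 successes into 24, and the choice of count could be made after the data are seen.

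**Working it through.** **Inputs (all from 9.1 unless noted).** Stage 1 has n1 = 13 and stops at r1 = 8 or fewer. Stage 2 adds n2 = 18, so N = 31. Success is 24 or more (r = 23). p0 = 0.65 and p1 = 0.85. The historical CR rate is 0.64 (2.4). The historical CRi share is not in the documents; it is assumed and shown as a range.

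**Formula.** The exact chance of declaring efficacy at a true rate p is

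P(declare | p) = Σ from x = 9 to 13 of [C(13, x) p^x (1−p)^(13−x)] × P(Y ≥ 24 − x), with Y ~ Binomial(18, p).

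**Step 1: reproduce the plan.** At p = 0.65 this gives 0.0951, as stated. At p = 0.85 it gives 0.9036, against a stated 90%. A search over two-stage designs with both error rates at 10% returns 8/13 and 23/31 as the minimax design. The design is computed correctly for a 65% null.

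**Step 2: vary the no-effect rate under the same rule.** The middle column is the no-effect rate minus 64.

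| No-effect CR/CRi rate | CRi points above 64% (assumed) | P(declare efficacy) |
|---|---|---|
| 64% | 0 | 0.0774 |
| 65% | 1 | 0.0951 |
| 66% | 2 | 0.1158 |
| 67% | 3 | 0.1398 |
| 70% | 6 | 0.2325 |
| 75% | 11 | 0.4534 |

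One point of CRi is absorbed by setting the null at 65%. Two points take the error above the planned 10%.

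The futility stop weakens as well. The chance of stopping at stage 1 is 0.4995 at 65% and 0.3457 at 70%. The chance of passing stage 1 with no effect therefore rises from 1 − 0.4995 = 0.50 to 1 − 0.3457 = 0.65.

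**Step 3: count CR only.** The null and the count then carry the same label, and 0.0951 stands at 65%. The 90% power then refers to an 85% rate of CR alone. If, as an illustration, 5 of those 85 points were CRi, the CR-only rate would be 80% and power would be 0.709.

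**Step 4: what a higher null would need, keeping N = 31 and the 8/13 stage 1.**
- Null 67%: 25/31, type I error 0.071, power at 85% 0.821.
- Null 70%: 26/31, type I error 0.062, power at 85% 0.681.

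Restoring 90% power for 70% against 85% with a minimax design takes r1/n1 = 15/22 and r/N = 40/52 (type I error 0.098, power 0.903). That is 52 − 31 = 21 more patients.

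**Step 5: can CR and CRi be told apart as printed?** In 12.1, CR is printed with platelets at or below 100 × 10⁹/L. CRi is printed with residual neutropenia given as ANC at or above 1.0 × 10⁹/L, the same ANC limit as for CR, and with the same platelet limit. As printed, the count limits do not separate the two categories.

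**The case against.** **Read literally, CR is tested against CR.** The hypothesis, H0, Ha, the final rule and the Schema endpoint all say CR, and 9.4.2 has no CRi category. On that reading 0.0951 is exact at 65%. This stands as arithmetic. It does not remove the problem, because 1.1.2 and both endpoint statements in 9.1 name CRi, and the plan would then test something other than its declared endpoint.

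**The 64% may already include CRi.** Section 1.1.2 uses complete remission as a label covering both, so CR in 2.4 could be shorthand for the same thing. This also stands as a possibility, and if it is so, a sentence in 2.4 and 9.1 settles the benchmark. It cannot be presumed, since 12.1 defines the two separately.

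**Two stronger readings are tempting.**
- A reader might infer that the 9.5% error is simply wrong. The documents do not show that. Inflation needs both that CRi counts as success and that the 64% excludes it, and neither is settled.
- A reader might also infer that pinometostat, infused through day 35, could raise the false-positive rate by delaying count recovery and turning CR into CRi. A patient moved from CR to CRi leaves the CR/CRi total unchanged, so the chance of reaching 24/31 does not move. Such a shift affects how a positive result is interpreted, not the type I error.

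**The stakes are limited.** Phase 2 seeks preliminary evidence at a 10% error rate and cannot open without an approved amendment. That lowers the urgency, but the amendment is also the natural place for the correction.

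**Conclusion.** The inconsistency is in the text: the endpoint is CR or CRi, the hypotheses and final rule are CR, stage 1 is undefined, and the benchmark is a CR rate of unstated scope. The null and decision rule are not shown to match the endpoint.

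The consequence is conditional. If CRi counts and the 64% excludes it, type I error exceeds 0.0951, and it exceeds 10% from two points of CRi upward. The documents cannot fix the amount, and nothing in them favours any row of the table. If only CR counts, the error rate holds at 65% and the stated endpoint goes untested.

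All these figures take the under-60 historical rate as applying to the enrolled patients. Eligibility starts at 14 with no upper age limit, so the true null could differ in either direction; that is a separate matter. Overall this is a should-fix, to be settled before phase 2 enrolment.

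**What to change.** In the amendment that 13.1 requires before phase 2:

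1. Reconcile the CR and CRi definitions in 12.1 so that the two can be separated, and give CRi a place in the 9.4.2 categories. Neither option below can be applied until this is done.
2. Use one definition of response in the null, at 9/13 and at 24/31. Either:
   - (a) count CR only against 65%, with CR/CRi as a secondary endpoint, and align 1.1.2 and 9.1; or
   - (b) count CR/CRi, state the historical under-60 rate on that same definition and, if it exceeds 65%, restate the null, cut-offs, type I error and power. If the 64% already includes CRi, say so in 2.4 and 9.1 and keep the design.
3. Report CR and CRi separately in either case.

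**Cost.** Option (a) is a text edit. Its downside is that the 90% power then refers to an 85% CR-only rate. Option (b) needs the under-60 historical cases re-tabulated. The protocol does not give the size of that subset or say that count-recovery data are available for it. If the null rises, the price is lower power at 31 patients (0.68 for a 70% null) or a larger trial.

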6.2 Definition of Dose-Limiting Toxicity

DLT Period. DLTs will be evaluated only in the Phase 1b – Safety Run-in Period. The period defined for evaluation of DLT is from the first day of pinometostat administration (day 1) to day 42 after induction, or if a re-induction was attempted, day 42 after re-induction.

Non Hematologic DLT will be determined based on non-hematologic Grade ≥ 3 toxicity related to the study drug alone or the study drug in combination with chemotherapy that occurs within first cycle of the combination. Severity of AEs will be graded according to National Cancer Institute Common Terminology Criteria for Adverse Events (CTCAE) v5. **With the following exceptions:** Grade 3 fatigue < 7 days; correctable electrolyte abnormalities within 72 hours; isolated, asymptomatic AST or ALT (<Grade 4) in the absence of significant bilirubin elevation (<Grade 3) that resolves within 7 days of drug hold; isolated, asymptomatic amylase elevation (<Grade 4) in the absence of lipase elevation (<Grade 3) that resolves within 7 days of drug hold. Pinometostat may be re-initiated in these patients at 60 mg/m² (no matter whether the patient was receiving 90 mg/m² or 60 mg/m²), and re-escalated (if patient was previously on 90 mg/m²; otherwise not applicable) if it does not recur; Grade 3 diarrhea that resolved to \leq Grade 1 or baseline in a week after receiving the maximal supportive therapy based on standard practice Grade 3 nausea and/ or vomiting (excluding need for TPN) that resolved to \leq Grade 1 or baseline in a week after the use of an optimal antiemetic regimen based on standard practice.

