Safety and tolerability evaluation and dose escalation for phase 1b will be performed in the usual 3+3 fashion. See Figure 1. Briefly, 3 patients will be enrolled on cohort 1. If zero of three patients experience dose-limiting toxicities (DLT) on pinometostat, proceed to enroll cohort 2. If one of three patients experience DLT, enroll an additional three patients for a total of six patients on cohort 1. If still only one of six total patients experience DLT, proceed to enroll cohort 2. If 2 or more (of either three total or six total patients) experience DLT, accrual will be stopped and a safety review and consideration of further dose level reductions will be discussed between PI, CTEP, and stakeholders. Cohort 2 will be evaluated likewise, except that no further dose level increases of pinometostat will be made, and if toxicity is unacceptable in cohort 2, the dosing plan of pinometostat for cohort 1 will move forward into the expansion phase. Otherwise, the dosing plan for cohort 2 will move forward into phase II expansion. The highest dose of pinometostat that is tolerated as described here will be considered the maximally tolerated dose (MTD).

[figure not shown]

Figure 1. A standard 3+3 dose escalation. With only two cohorts (dose levels), escalation stops

after cohort 2; if 2-3/3 DLT at dose level 1 (cohort 1), a safety review will be initiated to decide whether dose level reductions below the starting dose should be considered.

The phase 2 expansion phase will use the maximum tolerated dose/schedule as determined by phase 1b above and accrue additional patients to gather preliminary evidence of efficacy. Patients will be treated in the same manner as in the phase 1b portion above, with the exception that only a single dose level/cohort will be expanded.

The expansion cohort will comprise 4-25 patients who will be treated at the maximum tolerated dose schedule (see below; phase 1b patients who were treated at the MTD will be included in the statistical analysis of efficacy together with phase 2 patients, which in total comprises 10-31 patients).

Patients requiring re-induction, if any, will be treated at the assigned dose of pinometostat. Patients undergoing re-induction treatment will be analyzed jointly with patients not requiring re-induction for analysis of the primary efficacy endpoint, but a subgroup analysis consisting only of patients who did/did not require a second induction may be conducted.

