13.1 Study Oversight

This protocol is monitored at several levels, as described in this section. The Protocol Principal Investigator is responsible for monitoring the conduct and progress of the clinical trial, including the ongoing review of accrual, patient-specific clinical and laboratory data, and routine and serious adverse events; reporting of expedited adverse events; and accumulation of reported adverse events from other trials testing the same drug(s). The Protocol Principal Investigator and statistician have access to the data at all times through the CTMS web-based reporting portal.

For the Phase 1 portion of this study, all decisions regarding dose escalation/expansion/de-escalation require sign-off by the Protocol Principal Investigator through the CTMS/IWRS. In addition, for the Phase 1 portion, the Protocol Principal Investigator will have at least monthly, or more frequently, conference calls with the Study Investigators and the CTEP Medical Officer(s) to review accrual, progress, and adverse events and unanticipated problems.

For a Phase 1/2 trial, enrollment to the Phase 2 portion of the trial will not begin until a protocol amendment has been submitted which summarizes the Phase 1 results, the recommended Phase 2 dose, and the rationale for selecting it. The amendment must be reviewed and approved by CTEP before enrollment to the Phase 2 portion can begin.

During the Phase 2 portion of the study, the Protocol Principal Investigator will have, at a minimum, quarterly conference calls with the Study Investigators and the CTEP Medical

Officer(s) to review accrual, progress, and pharmacovigilance. Decisions to proceed to the second stage of a Phase 2 trial will require sign-off by the Protocol Principal Investigator and the Protocol Statistician.

All Study Investigators at participating sites who register/enroll patients on a given protocol are responsible for timely submission of data via Medidata Rave and timely reporting of adverse events for that particular study. This includes timely review of data collected on the electronic CRFs submitted via Medidata Rave.

All studies are also reviewed in accordance with the enrolling institution's data safety monitoring plan.

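### The selected schedule can enter the expansion on three DLT-assessed patients, although the plan's own expansion figures presume six, and DLTs are not counted after that

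*Combined protocol and SAP*

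**What the plan says.** Sections 6.2 and 9.1 describe the same 3+3 run-in with two cohorts. For cohort 1, section 9.1 says: "If zero of three patients experience dose-limiting toxicities (DLT) on pinometostat, proceed to enroll cohort 2". For the second: "Cohort 2 will be evaluated likewise, except that no further dose level increases of pinometostat will be made", and "Cohort 2 will comprise of 3-6 patients". If toxicity in cohort 2 is unacceptable, "the dosing plan of pinometostat for cohort 1 will move forward into the expansion phase". If not: "Otherwise, the dosing plan for cohort 2 will move forward into phase II expansion". A cohort grows to six only when one of its first three patients has a DLT. Neither section asks for six at the schedule that is finally selected.

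The accrual note in 9.1 confirms that either size is acceptable and links it to the efficacy design of 13 patients in stage 1 and 31 in all: "Patients treated at the maximum tolerated dose in the phase 1b portion (3, or 6) will be counted toward the total needed".

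On what follows, section 6.2 says: "DLTs will be evaluated only in the Phase 1b – Safety Run-in Period". Section 13.1 adds a checkpoint: "enrollment to the Phase 2 portion of the trial will not begin until a protocol amendment has been submitted". That amendment summarizes the phase 1 results and needs CTEP approval, but no minimum number of patients at the selected schedule is set.

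Section 9.1 also gives an expansion of 4-25 patients and an efficacy total of 10-31. The enrollment tables in 9.2 plan 12 patients in phase 1b and 25 in phase 2.

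**The concern.** Objective 1.1.1 is to determine a safe and tolerable schedule. If three patients without a DLT are enough, that conclusion rests on very little, and up to 31 - 3 = 28 further patients are then treated with no DLT count. The fallback is the weakest case: cohort 1 can go forward on three patients just after the neighboring schedule has failed, with no requirement to return and complete it. The only numerical stopping rule in phase 2 is the futility rule on remissions, which does not address toxicity.

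There is also a plain inconsistency. The note that allows three carried-over patients does not fit the expansion size or the planned phase 2 enrollment.

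**Working it through.** **1. The plan's own figures.** Inputs from 9.1: stop at 8 or fewer of 13, success at 24 or more of 31, null rate 0.65, alternative 0.85. The probability of success is the sum over x = 9 to 13 of P(X1 = x | 13, p) times P(X2 >= 24 - x | 18, p). It is 0.0951 at p = 0.65 and 0.904 at p = 0.85, in agreement with the stated 0.0951 and 90%. The maximum accrual, 12 + 31 - 6 = 37, also reproduces.

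**2. How many carried-over patients the figures presume.**
- Expansion against efficacy total (9.1): 10 - 4 = 6 and 31 - 25 = 6.
- Enrollment tables (9.2): 12 + 25 = 37, which matches the maximum only with six carried over.
- With three carried over: the expansion would need 31 - 3 = 28, but 3 + 25 = 28 in total, three short of 31.

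**3. What three or six patients show.** One-sided 95% exact (Clopper-Pearson) upper limits for the DLT rate:
- 0 of 3: 1 - 0.05^(1/3) = 63%.
- 0 of 6: 1 - 0.05^(1/6) = 39%.
- 1 of 6, which the existing criterion also accepts: 58%.

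**4. Chance that a cohort clears.** The documents give no target DLT rate, so the rates below are assumptions. For context, section 2.2.3 reports DLTs in 4 of 18 children on the single agent (22%), a different setting. With true rate p:
- current rule: (1-p)^3 + 3p(1-p)^5
- at most one DLT in six: (1-p)^6 + 6p(1-p)^5

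| Assumed DLT rate | P(0 of 3) | Clears, current rule | Clears, at most 1 of 6 | Fall |
|---|---|---|---|---|
| 10% | 0.729 | 0.906 | 0.886 | 0.020 |
| 20% | 0.512 | 0.709 | 0.655 | 0.053 |
| 30% | 0.343 | 0.494 | 0.420 | 0.074 |
| 40% | 0.216 | 0.309 | 0.233 | 0.076 |
| 50% | 0.125 | 0.172 | 0.109 | 0.063 |

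Dividing the second column by the third, 69-73% of clearances rest on three patients at rates of 20-50%, and about 80% at 10%. The fall in the last column is exactly the chance of no DLT in the first three patients followed by two or more in the next three.

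**5. Accrual if the selected cohort is filled to six.**
- Schedule retained: the expansion drops from 28 to 25, and stage 1 patients still to enroll drop from 13 - 3 = 10 to 13 - 6 = 7. The efficacy total stays 31, so type I error and power do not move. The trial total is the other cohort plus 31, that is 34 or 37, as before.
- Cohort 2 clears on 0 of 3, is filled, then fails, and cohort 1 goes forward: cohort 2's six patients do not count toward the 31, so the total is 6 + 31 = 37. Without filling it would have been 3 + 31 = 34 had cohort 1 held three patients. This costs up to three extra patients. The chance that cohort 2 follows this path is the fall in the table, 5-8% at rates of 20-50%.

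**The case against.** The case for leaving the plan alone has several parts.

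- *This is an ordinary 3+3.* True, and clearing on three patients is not an error in itself. The text calls itself brief and points to a flow chart that could not be read in the copy reviewed. Even if the chart asked for six, the accrual note would still allow three.
- *Safety is not unwatched in phase 2.* This stands. A reader might infer that toxicity monitoring stops with the run-in, but the documents say otherwise. CTCAE toxicity is collected in every treated patient (9.1, 9.3, 9.4.1), section 7 has patient-level rules by grade, and CTEP must approve the amendment before phase 2 (13.1). Section 13.3 adds two-weekly teleconferences, committee review of serious events, and review by the principal investigator of whether to end the trial. Section 9.1 also lets the principal investigator add patients at a level for safety. What is missing is narrower: a required minimum at the selected schedule and a running DLT count.
- *Cohort 2 does not rest on three patients alone.* Largely right. Both cohorts share the pinometostat plan for days 1-7 and the same chemotherapy, so when cohort 2 is selected at least six patients have been assessed at that schedule or the lower one. This is why the fallback to cohort 1 is the sharper case.
- *Six patients are not much better.* Partly right. A permitted 1 of 6 leaves an upper limit of 58%, close to the 63% after 0 of 3, and at a 20% DLT rate a possibly acceptable schedule is lost about 5 percentage points more often.

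**Conclusion.** The point holds in a limited form. The text allows expansion on 0 of 3, DLTs are not evaluated afterwards, and the accrual note conflicts with the expansion range and the phase 2 enrollment table. The inconsistency needs no assumption. The size of the safety gain depends on assumed DLT rates and is modest: about 6 to 8 percentage points fewer clearances at 30-50%, against 2 points at 10% and 5 points at 20%. These are per-cohort figures; cohort 2 is reached only if cohort 1 has cleared first.

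Two stronger conclusions are not supported. Filling to six is not free of patients on every path, because a filled cohort 2 that then fails can add up to three, still within 37. Nor would six patients settle tolerability, since one DLT in six remains compatible with a high rate. That second limit is the reason to keep a DLT tally during the expansion.

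**What to change.** Reconcile the expansion range and accrual note in 9.1 with the table in 9.2, and state the requirement in both 6.2 and 9.1. Possible wording: Before the expansion opens, six patients will have been DLT-assessed at the selected schedule and judged by the existing criterion of no more than one DLT in six. If cohort 1 is selected because cohort 2 failed, cohort 1 is first completed to six. These six patients count toward stage 1 of the efficacy design.

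In addition, keep recording events that meet the 6.2 definition during the expansion, and show the cumulative count at the phase 2 calls in 13.1.

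Cost: protocol wording and time. One more DLT window is about 6 to 8 weeks (day 42, or day 56 for a provisional hematologic DLT), longer with re-induction. The amendment in 13.1 must summarize the phase 1 results, so this time probably comes before its submission and should not be assumed to overlap with it. The possible three extra patients on the cohort 2 path should be stated alongside the 37-patient maximum.
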